We propose to perform a prospective, randomized, double-blind placebo controlled trial. Patients will be included if they are: 1) receiving outpatient hemodialysis at the James J. Peters VAMC, 2) receiving IV vitamin D therapy according to National Kidney Foundation guidelines, 3) between the ages of 45-89 years, 4) a veteran outpatient or stable community living center patient, and 5) able to ambulate independently or with an assistive device for at least 20 feet. Exclusion criteria include: 1) 25-OH vitamin D level \geq 25 ng/ml, 2) hypercalcemia, 3) active malignancy within 6 months, 4) receiving intravenous antibiotics for infection, 5) history of dementia, 6) hemoglobin $<$ 8.5g, 7) history of conditions that interfere with postural instability (e.g. cerebellar disease, vestibular disease or any others that may present), and 8) poor compliance with dialysis treatments (history of skipping \geq 2 treatments per month for $>$ 2 months). A 25-OH vitamin D level of $<$ 25 ng/ml level was chosen based on previous studies that have shown that patients have the greatest improvement in muscle strength when levels below this threshold are increased. Patients will first be identified based on the inclusion criteria, then informed about the study and consented. Those who meet the exclusion criteria will be randomized to treatment or placebo. Enrolled participants will be randomized 2:1 to receive vitamin D (n=20) or placebo (n=10) for 6 months. All participants will be tested twice over two weeks to establish baseline values. Following baseline testing, the treatment group will receive 50,000 IU (standard replacement therapy) of oral cholecalciferol or placebo. The initial dose of cholecalciferol will be 50,000 IU weekly for 6 weeks. Vitamin D levels will then be measured. Participants who still have Vitamin D insufficiency (\leq 35 ng/ml) will remain on 50,000 IU of cholecalciferol for another 6 weeks, at which point Vitamin D levels will be measured again. Participants who reach 25-OH levels $>$ 35 ng/ml will have their dosing regimen lessened to 10,000 IU weekly (maintenance dose) for the remainder of the 6 months. Participants receiving placebo will start taking the placebo maintenance dose after the first 6 weeks. For safety monitoring, 25(OH) vitamin D₃ levels will also be re-measured at monthly intervals and followed by an independent medical monitor. In patients who have serum vitamin D levels \geq 60

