ng/ml, the frequency of administration will be reduced to once a month. The participants will receive supplementation for a total of 6 months. At this time, vitamin D levels will be reassessed and participants will undergo follow-up functional assessments, and cognitive and immune testing. Subjects will be recruited from the outpatient hemodialysis (HD) unit which is located on the fourth floor of the James J. Peters VAMC.

Primary Outcomes (tested at Baseline, 3 months and 6 months):

- 1) Neuromuscular functional performance using the 50ft timed walk, the TUG, a timed stair climb, and the Chair Raise test, (48)
- 2) Postural stability using a Sway meter (NeuroCom International, Inc., Clackamas, OR) that measures displacement of the body at the level of the waist in 30 second periods (49) and the Functional Reach test.
- 3) Muscle hand grip strength using the Harpenden Hand Grip dynamometer (50) and hip flexor and knee extensor strength using a Push-Pull Muscle Strength dynamometer.

Secondary Outcomes:

- 1) Cognitive function (tested at Baseline, 3 and 6 months):
 - a) Mental Status: Mini-Mental Status Exam (MMSE) (51) and Short Blessed Test (SBT) (52);
 - b) Memory: California Verbal Learning Test – II (CVLT-II) (53);
 - c) Language: Category Fluency and Controlled Oral Word Association Test (COWAT) (54);
 - d) Attention and Processing Speed: Trails A (55), Digit Span (56), Symbol Digit Modality Test (SDMT) (57), and Stroop Color and Word (58)
 - e) Executive Function: Trails B (55) and Stroop Color-Word (58).
- 2) Self-assessment of Physical Fxn and Health (tested at Baseline, 3 months and 6 months):
 - a) Physical Activity Scale for Persons with Physical Disabilities (PASIPD) (59)
 - b) NIH PROMIS (v1.0 Item Banks): Global Health Physical Function, Pain, Fatigue, Sleep, Emotional Distress (60)
 - c) Beck Depression Inventory (BDI)
- 3) Immunology (tested at Baseline, 6 months)
 - a) Serum cytokines

This study will be performed over two years.

TABLE 1. Study Flow Sheet	BL 1	BL 2	Month 1	6 weeks	Month 2	Month 3	Month 4	Month 5	Month 6
Week:	0	0 ₂	4	6	8	12	16	20	24
Physical Function Assessment 50ft walk, TUG, stair climb, Chair Raise, Functional Reach, Sway, Hand Grip, Hip & Knee Strength		X				X			X
Self - Assessment PASIPD & NIH PROMIS (short forms): Physical Fxn, Pain, Fatigue, Global Health, Sleep, Emotional Distress, BDI		X				X			X
Cognitive Impairment Tests									

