Mental Status: Mini-Mental Status Exam (MMSE) (for screening), Short Blessed Test (SBT)		X							X
Executive Function: Trails B, STROOP Color-Word		X							X
Memory: California Verbal Learning Test (CVLT-II)		X							X
Attention & Processing Speed: Trails A, DS WAIS-III, SDMT, StroopColor, Stroop Word		X							X
Language: Category Fluency, Controlled Oral Word Association Test		X							X
Metabolic & Endocrine Tests	X	X	X	X	X	X	X	X	X
Vitamin D Monthly Renal Clinic labs (chart review) B12 Folate		X	X		X	X	X	X	X
Immune Function Tests serum cytokines		X							X
Demographic Data & Health Monitoring									
Age, Height, Weight, BMI, Co-morbidities, HD Hx (chart review)		X							X

Power analysis: We expect that vitamin D supplementation will improve muscular function and strength. Using information from the limited studies reported in the literature, Pfeifer, et al. (25) reported an 11% decrease in the timed up and go test for individuals treated with Vitamin D replacement therapy compared with placebo who had an average decrease. We believe our study subjects will respond in a similar manner and have powered our study such that we expect 15 of 20 subjects in the treatment group to achieve an 11% decrease in the TUG test, consistent with the Pfeifer, et. al. study findings. Similarly, postural sway has been reported by two different groups to decrease by 9% (24) and 28% (25). To be conservative, we have chosen an expected 15% decrease in postural sway in our study subjects. Muscle strength as measured by hip extensor has been reported to improve by 16% (26), and by knee extensor strength gains from 8% to 25% (25, 26). Therefore to be on the conservative side, we have

hypothesized a 10% muscle strength increase in hand grip and hip flexor strength. Only 1 of 10 in the placebo-control group is anticipated to demonstrate these improvements.

We estimate power for a two-sided test using a continuity correction. At an alpha of 0.05, with treatment response of 75% and placebo response of 10%, we estimate 90% power for a sample size of 26; 80% power with a sample size of 22 and 70% power for a sample size of 18. We are proposing a sample of 30 permitting 33% drop out to permit us to maintain reasonable power for a pilot study.

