The primary analysis for functional and cognitive outcomes will use the responder analysis described above. Additional secondary analyses will be performed on the primary outcome variables. In the first analysis, the percent change variables will be used for the group comparisons and analyzed by one-way analysis of variance (ANOVA) ($Y_1 = \%$ change; $X_1 = \text{Group}$). The percent change variable has the advantage of being easily analyzed in an analysis of covariance (ANCOVA) model if controlling variables are identified. For example, years on hemodialysis (HD y) may be need to be controlled for and as such this model would be $Y = \%$ change; $X_1(\text{HD y}) + X_2(\text{Group})$. The second analysis to be performed on the primary outcome variables will be the more traditional two-factor mixed model (2x3 table), where the between factor is Group (treatment, placebo) and the repeated measures (i.e. the within-subjects) factor is Time (BL, 3 and 6 months). In the case of missing data we will use 2 imputation methods. First as is commonly done in clinical trials of cognitive impairment and dementia we will use the last observation carried forward for missing terminal visits. We will compare results from these methods with a variety of other imputation methods. For missing data within a specific test, we will assign the average the remaining domains for those that do not complete a domain. Other imputations will include assigning values from 1) a regression across the available time points, and 2) assigning the average value of all subjects within in the group. We will compare results using these different imputations.

Significant main effects will further be explored by single degree of freedom post hoc analyses. For the secondary analyses covariates will be used including age and education adjusted T scores will be used for the baseline versus 6 month comparisons by performing a 2x2 repeated measures ANOVA. For

the self assessment variables (PASIPD and NIH PROMIS) percent change will be calculated as previously described and analyzed by one-way ANOVA as described for the primary outcome variables above.

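### The stated power figures fit 1:1 rather than the planned 2:1 allocation, and the primary responder analysis lacks cut-offs for most outcomes, a single lead outcome, a visit and a multiplicity rule

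*Combined protocol and SAP*

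**What the plan says.** **Primary analysis.** The Statistical Analysis Plan says: "The primary analysis for functional and cognitive outcomes will use the responder analysis described above". Continuous analyses are labelled secondary: "In the first analysis, the percent change variables will be used for the group comparisons and analyzed by one-way analysis of variance", followed by a two-factor mixed model over baseline, 3 and 6 months.

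**Responder figures.** The only responder description before that sentence is the Power analysis paragraph.
- TUG: "we expect 15 of 20 subjects in the treatment group to achieve an 11% decrease in the TUG test".
- Sway: "we have chosen an expected 15% decrease in postural sway in our study subjects".
- Hand grip and hip flexor strength: a 10% gain.
- Placebo: one patient in ten is expected to show these improvements.

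**Power.** "We estimate power for a two-sided test using a continuity correction". At alpha 0.05 with 75% versus 10% response, "we estimate 90% power for a sample size of 26; 80% power with a sample size of 22", and 70% at 18. Thirty patients are proposed, permitting 33% dropout.

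**Allocation.** Research Design and Methods: "Enrolled participants will be randomized 2:1 to receive vitamin D (n=20) or placebo (n=10) for 6 months". The Statistical Analysis Plan repeats 2:1, in blocks of six.

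**Outcomes and visits.** The outcome list is headed "Primary Outcomes (tested at Baseline, 3 months and 6 months" and covers the nine functional measures of SA1. H1 singles out postural sway. H2 speaks of improvement in cognition without a threshold. The paragraph before the Statistical Analysis Plan calls the cognitive tests secondary, with exploratory analyses expected.

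**The concern.** Two separate things look wrong.

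First, the response rates in the power paragraph come from counts in a 20:10 trial (15/20 = 75%, 1/10 = 10%), yet the sample sizes beside them look like equal-arm totals. If so, they overstate the power available at those totals. That matters most once dropout brings the trial down to about 20 patients, which is the situation the extra enrolment is meant to cover.

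Second, an analyst cannot run the primary analysis from the text. Most functional outcomes and every cognitive test lack a responder definition, the comparison test is not named in the analysis section, and lead outcome and visit are open. Two careful analysts could report different primary results, and the choice could be made after the data are seen. Feasibility is a stated goal of this pilot, but it also powers a two-sided 0.05 efficacy test, so the definition of that test should be fixed.

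**Working it through.** **Inputs.** p1 = 0.75, p0 = 0.10, two-sided alpha 0.05 and continuity correction (Power analysis); 20:10 allocation (Research Design and Methods); 33% dropout (Power analysis). Difference d = 0.65; k = placebo/vitamin D ratio.

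**Formula (Fleiss, pooled variance, continuity-corrected).**
- n = [1.960·√(p̄(1−p̄)(1+1/k)) + z_power·√(p1(1−p1) + p0(1−p0)/k)]² / d², where p̄ = (p1 + k·p0)/(1+k)
- n_cc = (n/4)·[1 + √(1 + 2(1+1/k)/(n·d))]², per vitamin D arm; total = n_cc(1+k)

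**Reproducing the plan's figures at 1:1 (k = 1).** p̄ = 0.425; the two square roots are 0.6991 and 0.5268. For 90% (z = 1.2816): n = 9.90, n_cc = 12.79, total 25.6. For 80% the total is 21.3 and for 70% it is 18.5. Against the stated 26/22/18, the first two agree after rounding up to whole arms. The third is looser: strict rounding gives 20, and 9:9 has 68% power.

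**Same formula at 2:1 (k = 0.5).** p̄ = 0.5333; the square roots are 0.8641 and 0.6062. For 90%: n = 14.45, n_cc = 18.78, total 28.2. For 80% and 70% the totals are 23.7 and 20.7. In whole patients this is 29/24/21, or 30/24/21 in complete 2:1 sets.

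**Power at given sizes.** Power = Φ{[d − ½(1/n1+1/n0) − 1.960·SE0]/SE1}, with SE0 the pooled and SE1 the unpooled standard error. Example, N = 26 at 2:1: (0.65 − 0.0865 − 1.960 × 0.2075)/0.1456 = 1.076, so 85.9%.

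| N | Stated | 1:1 | 2:1 |
|---|---|---|---|
| 26 | 90% | 90.7% | 85.9% |
| 22 | 80% | 82.1% | 74.7% |
| 18 | 70% | 68.0% | 58.2% |

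The shortfall at 2:1 is 4 to 12 points.

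**Planned size and dropout.**
- 20:10: (0.65 − 0.075 − 1.960 × 0.1932)/0.1356 = 1.448, so 92.6%. Exact enumeration gives 92.1% with the continuity correction (Yates) and 92.7% with Fisher's test.
- 33% dropout leaves 30 × 2/3 = 20 patients. With no value kept from dropouts: 67.1% at an exact 2:1 split. At 13:7 it is 68.8% by formula, 69.9% by exact Yates and 72.8% by Fisher. The range is about 67-73%.

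**Coverage of the responder definition.** SA1 and the outcome list name nine functional measures; the percent-change list in the Statistical Analysis Plan has eight entries. Figures exist for TUG, sway, hand grip and hip flexor. None is given for the 50 ft walk, stair climb, Chair Raise, Functional Reach or knee extensor strength, or for any cognitive test. Percent change is computed at both 3 and 6 months and neither visit is chosen.

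**Cost of dichotomising, on the plan's own rates.** The documents give no SD, so assume normal changes with equal SD. Then 75% versus 10% implies a standardised difference of 0.674 + 1.282 = 1.956. A t-test at 20:10 (28 df, noncentrality 5.05) has 99.8% power. The responder test has 92.1% (Yates), 92.7% (Fisher) or 97.0% (uncorrected): a loss of about 3 to 8 points.

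**The case against.** **The 1:1 basis is not stated.** It is inferred, and the 70% figure fits it only loosely. A one-sided 2:1 calculation gives 24/21/18, but the text says two-sided. Fisher's exact test at 2:1 splits gives 91.7% (17:9), 75.7-84.7% (15:7 or 14:8) and 74.8% (12:6), broadly the stated values. However, the text specifies a continuity correction, and under that reading the mismatch stands.

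**It hardly matters at N = 30.** This is right for full retention. A reader might infer that the trial is underpowered or needs more patients; at 92-93% on its own assumptions, the documents do not support that.

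**The dropout figure is pessimistic.** The plan carries the last observation forward. In simulation (7 of 20 and 3 of 10 leaving, visit correlation 0.7, no mean change on placebo), carrying month 3 gives 73/77/86% (Yates/Fisher/uncorrected) if half the effect is present by then, and 92/93/97% if all of it is. If only baseline can be carried, it is 50/66/70%. The 67-73% is therefore a no-value-kept case, not a forecast.

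**Only TUG has a true per-subject cut-off.** A reader might infer this, because sway is worded as an expected decrease. But the placebo sentence counts patients showing these improvements, so all four figures can be read as cut-offs.

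**Error inflation.** A reader might infer serious false-positive inflation. Under the plan's own 10% placebo rate and a continuity-corrected test, simulated family-wise error over 8 to 18 tests is only 2-4% (outcome correlation 0.3-0.7 and visit correlation 0.7, both assumed). Much higher values need an uncorrected test or a higher null response. What remains is the missing rule.

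**The visit is partly settled.** The flow sheet and the procedures list test cognition only at baseline and 6 months, although the secondary-outcome list adds 3 months. The ambiguity is mainly functional.

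**Immediate clinical implementation.** The rationale mentions this alongside a future larger study. It is not a decision rule, and nothing here rests on it.

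**Conclusion.** The point holds in two parts.

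1. **Power.** Under the stated two-sided, continuity-corrected test, 26/22/18 patients at the planned 2:1 give about 86/75/58% power, not 90/80/70%; the stated powers need about 29-30/24/21. That the authors used 1:1 is inferred. The planned 20:10 is adequate at about 92-93% if 75% versus 10% holds. At the permitted dropout, with no value kept, power is about 67-73%.

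2. **Definition.** The primary responder analysis covers four of nine functional outcomes and no cognitive test. Its lead outcome differs between H1 and the power analysis, its functional visit is not chosen, its test appears only through the continuity correction in the power text, and no multiplicity rule is given. Giving cognition a primary analysis conflicts with calling it secondary and exploratory.

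A reader might go further and call the responder analysis itself an error. The documents do not support that: continuous analyses are already planned as secondary, and on the plan's own rates the cost is about 3-8 points at 20:10. Larger losses require a lower response or dropout as further assumptions. The changes should be made, but they clarify and correct the plan; they do not call the design into question.

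**What to change.** Before unblinding, amend the Power analysis and Statistical Analysis Plan:

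- **(a)** Restate power for 2:1 (about 86/75/58% at 26/22/18, or 29-30/24/21 for 90/80/70%), for 20:10 (about 92-93%), and for the permitted dropout with the missing-data assumption stated. N stays at 30.
- **(b)** Name one primary outcome and visit: for example sway at 6 months, in line with H1, or another single choice by the sponsor. Treat the other functional outcomes, the 3-month visit and cognition as supportive or exploratory, with confidence intervals. For cognition this follows what the plan already says.
- **(c)** Limit the responder analysis to TUG, sway, hand grip and hip flexor. Write each figure as a per-patient cut-off and name a test that matches the power text.
- **(d)** As an improvement to consider, analyse the chosen outcome by ANCOVA of the 6-month value on arm and that outcome's own baseline.

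The cost is a text amendment, with no new patients, visits or data. The other outcomes lose primary status, and the stated power becomes slightly less favourable. If (d) is adopted as primary, H1 and the power basis must also be reworded.

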There is little information on the effect of vitamin D replacement therapy and change in cognitive function. Based on previous studies that demonstrated a correlation between poor performance and vitamin D deficiency, we expect vitamin D supplementation to improve SBT and MMSE scores (27, 30, 61). Of note, the cognitive function tests are our secondary outcome variables and we expect to gain empirical information after performing exploratory analyses regarding the effect of vitamin D replacement on cognitive function as part of this pilot study. A demonstration of improvement in neuromuscular and/or cognitive function would lead to the immediate implementation in clinical practice of 25-OH vitamin D supplementation in the care of HD patients who are vitamin D deficient and a future larger study to demonstrate dosing and length of time for maintenance of sufficient vitamin D levels to retain this positive effect.

Statistical Analysis Plan: Subjects will be randomized in a prospective, two-group, randomized study design utilizing a convenience sample of patients on hemodialysis. Subjects will be randomized to the treatment (Vit D) or placebo groups using a 2 to 1 block randomization determined from a web-based program (<http://www.randomization.com>). Subjects will be grouped in order of consenting such that the first 6 subjects will be in block 1, the next 6 in block 2, and so on. Five blocks will be performed. Each block will contain 6 subjects (2:1), with 4 subjects being randomized to vitamin D treatment to 2 subjects being randomized to the control group. Percent change scores will be calculated for both time points after treatment (3 or 6 month values – Baseline)/ Baseline * 100 for all primary outcome dependent variables (50ft timed walk, TUG, timed stair climb, Chair Raise, Functional Reach, postural sway, handgrip strength, and flexor/abduction strength) for each subject in both groups.

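### The percent-change ANOVA, a secondary analysis of the functional outcomes, does not pre-specify the outcome's own baseline as a covariate, so chance imbalance goes uncorrected and a little power is lost

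*Combined protocol and SAP*

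**What the plan says.** All references are to the combined protocol and SAP, Section C.

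- **Outcome scale.** Under Statistical Analysis Plan: "Percent change scores will be calculated for both time points after treatment", as follow-up minus baseline, divided by baseline, for each functional test.
- **Rank of the analysis.** "The primary analysis for functional and cognitive outcomes will use the responder analysis described above. Additional secondary analyses will be performed on the primary outcome". The ANOVA is the first of these secondary analyses.
- **Model.** "the percent change variables will be used for the group comparisons and analyzed by one-way analysis of variance (ANOVA", with group as the only term.
- **Covariates.** "The percent change variable has the advantage of being easily analyzed in an analysis of covariance (ANCOVA) model if controlling variables are identified". The one illustration is "For example, years on hemodialysis (HD y) may be need to be controlled for". No selection rule is given.
- **Second secondary analysis.** A two-factor model in which "the repeated measures (i.e. the within-subjects) factor is Time (BL, 3 and 6 months". Baseline is a level of the response here, not a covariate.
- **Self-assessments.** PASIPD and PROMIS go to the same one-way ANOVA on percent change.
- **Availability of baseline.** The Primary Outcomes list has every functional test done at baseline, 3 and 6 months, and Table 1 places the physical assessment at one baseline visit. Research Design and Methods says "All participants will be tested twice over two weeks to establish baseline values", but Basic Information item 1 applies the double testing to serum vitamin D. Either way, at least one functional baseline exists.

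**The concern.** Percent change looks as if it already accounts for baseline, but it does not. A patient whose baseline is poor partly through measurement error or a bad day tends to move back towards the average, and the smaller or larger denominator does not cancel this. Percent change therefore stays negatively correlated with baseline. For timed tests and sway (lower is better), an arm that starts high shows a larger percent fall. For strength and reach (higher is better), an arm that starts low shows a larger percent rise. In both cases the arm that starts worse appears to benefit more.

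Randomisation is in blocks of 6 with no stratification by function described, and one arm has only 10 patients, so sizeable imbalance is not rare. At stake are the effect estimates that the pilot would pass to a pivotal trial, and some precision that could be had from data already collected. Leaving the covariate open also means that it could be chosen after the data are seen.

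**Working it through.** **The plan's own figures.** The plan gives no power figure for this ANOVA. Its power statement (Power analysis) concerns responders: 75% versus 10%, two-sided alpha 0.05, continuity correction, total N of 26, 22 and 18 for 90%, 80% and 70% power. The continuity-corrected two-proportion formula with equal arms gives 26, 22 and 20. These figures use neither a continuous SD nor a baseline correlation, so nothing below changes them.

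**Inputs from the documents.** 20 versus 10 patients; planned changes of 11% (TUG), 15% (sway) and 10% (grip and hip flexor strength).

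**Assumptions, because the documents give neither.** Log-normal outcomes, CV 20% to 40%, baseline-to-follow-up correlation ρ of 0.5 to 0.85, equal variance at both times.

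**1. How often imbalance arises.** The SD of the difference in mean baseline, in baseline SDs, is √(1/20 + 1/10) = 0.387. The probability of a difference above 0.5 SD in either direction is 2 × [1 − Φ(0.5/0.387)] = 0.197, about 20% per test.

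**2. What it does to the contrast.** With log-scale SD σ = √ln(1 + CV²) and imbalance d, the expected shift with no true effect is about −(1 − ρ) × σ × d.
- CV 20%: σ = √ln(1.04) = 0.198. At d = 0.5 the shift is 0.5 × 0.198 × 0.5 = 5.0 points at ρ = 0.5, and 0.3 × 0.198 × 0.5 = 3.0 points at ρ = 0.7.
- CV 40%: σ = √ln(1.16) = 0.385. The shift is 9.6 points at ρ = 0.5 and 5.8 at ρ = 0.7. Simulation on the percent scale gives about 10 and 6.
- At ρ = 0.85 simulation gives about 1.5 to 3 points.

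With baseline as a covariate, the simulated shift is about 1 point or less in every null setting. The correlation of percent change with baseline was about −0.26 to −0.48 in those settings.

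**3. Precision.** On the log scale, the variance of change is 2σ²(1 − ρ) and the ANCOVA residual variance is σ²(1 − ρ²). Their ratio is (1 + ρ)/2: 0.75 at ρ = 0.5, 0.85 at 0.7, 0.925 at 0.85.

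**4. Power at the protocol's own effects** (40,000 simulated trials per cell, 20 versus 10; percent-change ANOVA → percent change with baseline covariate):

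| Effect | CV | ρ = 0.5 | ρ = 0.7 | ρ = 0.85 |
|---|---|---|---|---|
| 11% | 20% | 32% → 38% | 49% → 53% | 77% → 79% |
| 11% | 40% | 13% → 14% | 17% → 19% | 29% → 30% |
| 15% | 20% | 54% → 64% | 76% → 80% | 96% → 97% |
| 15% | 40% | 20% → 22% | 28% → 31% | 50% → 51% |

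ANCOVA of the log follow-up value on log baseline gives results within about 1 point of the adjusted column.

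**5. Type I error.** With no effect, both methods reject in about 5% of trials in every setting.

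**The case against.** The strongest reply is that little hangs on this. The analysis is secondary, in a 30-patient feasibility pilot, behind a responder analysis that sets the sample size. That stands, and it limits how serious the point is.

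Second, the test is valid over repeated randomisation, and a 0.5 SD imbalance is absent in about four trials in five for a given test. That also stands. The error is conditional on the imbalance that happens to occur. A reader might infer an inflated false-positive rate, but the calculations show none overall.

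Third, the plan may already allow the remedy: years on HD is only an example, and percent change is described as "easily analyzed in an analysis of covariance (ANCOVA) model if controlling variables are identified". This stands in part. Baseline is not forbidden, so the fault is that it is neither named nor governed by a rule. The group-by-time model does not fill the gap, because it compares unadjusted changes. The sentence on age- and education-adjusted T scores concerns a baseline versus 6-month comparison and does not name the functional baseline. Baseline 25-OH vitamin D is a candidate confounder for the immune analysis only.

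Fourth, percent change matches the thresholds in the power statement, so abandoning it would be a loss. This stands as well. A reader might infer that percent change must go, but the fault is cured by adding one term.

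**Conclusion.** The point holds as a modest, inexpensive improvement to a secondary analysis. The functional baseline is collected but is not a pre-specified covariate in either continuous analysis, and dividing by it is no substitute.

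The larger consequence is conditional bias. In about 20% of randomisations per test, imbalance exceeds 0.5 SD. An imbalance of that size moves the contrast by 5 to 10 points at correlation 0.5 and 3 to 6 at 0.7, against planned effects of 10% to 15%. The power gain is smaller: about 10 points at best (15% effect, CV 20%, correlation 0.5), 1 to 2 points at the 11% effect with CV 40%, 3 or less at the 15% effect with CV 40%, and almost nothing when the correlation is high. All of these sizes rest on the assumed CV, correlation and log-normal shape.

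A reader might infer that the trial's main conclusion or its sample size is compromised, or that power is substantially lost across the board. The documents do not support this. The responder comparison is primary, the sample size comes from response proportions, and the planned 11% and 15% effects yield small gains in most settings.

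**What to change.** In the Statistical Analysis Plan, before unblinding:

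- State that each continuous between-group comparison of a functional test, at 3 months and at 6 months, includes that test's baseline value as a covariate.
- Choose the form for each outcome in advance. Either add baseline to the percent-change ANCOVA already provided for, or use ANCOVA of the follow-up value on arm and baseline. In the second form, use the log scale where the outcome is skewed and back-transform to a percent difference. The two are not algebraically identical but perform much alike, and both keep a percent scale.
- Apply the same rule to the PASIPD and PROMIS comparisons.
- Say whether years on HD is included, or give the rule for deciding.

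The responder analysis, the group-by-time model and the sample size can stay as they are for this purpose. The cost is a few sentences and one degree of freedom: with 30 patients, residual degrees of freedom fall from 30 − 2 = 28 to 30 − 3 = 27. No new data are needed.

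### Group-mean filling of missing values makes the secondary percent-change ANOVA reject too often, so it can lend false support as a sensitivity check

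*Combined protocol and SAP*

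**What the plan says.** The Statistical Analysis Plan (section C) makes a responder comparison primary: "The primary analysis for functional and cognitive outcomes will use the responder analysis described above". One-way ANOVA on percent change by group, and a Group by Time model over baseline, 3 and 6 months, are secondary. "Percent change scores will be calculated for both time points after treatment", and the visit at which response is judged is not named.

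The missing-data text follows the two secondary analyses but opens in general terms. LOCF comes first: "we will use the last observation carried forward for missing terminal visits". A gap within a test is filled from the participant's remaining domains. Then: "Other imputations will include assigning values from 1) a regression across the available time points", and second, "assigning the average value of all subjects within in the group". Results under the different fills are to be compared. The text does not say whether the group mean replaces the raw 6-month value or the percent-change score.

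The Power analysis adds: "We estimate power for a two-sided test using a continuity correction", with 75% vs 10% response and alpha 0.05; "80% power with a sample size of 22 and 70% power for a sample size of 18" (and 90% at 26); and "We are proposing a sample of 30 permitting 33% drop out to permit us to maintain reasonable power for a pilot study".

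**The concern.** A missing value replaced by its arm's mean lies at the centre of that arm. It adds nothing to the sum of squares, yet it adds one to the sample size and one to the residual degrees of freedom. The ANOVA then reports a standard error that is too small and rejects a true null hypothesis more than 5% of the time.

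The method is offered as a check on the others. A check with false precision can appear to confirm a finding that the observed data do not support. The plan allows for up to a third of participants to be lost, so the number of filled values could be large relative to 30.

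**Working it through.** **Inputs from the documents.** Arms of 20 and 10; two-sided alpha 0.05; response 75% vs 10%; continuity-corrected test; drop-out allowance 33% (10 of 30). **Assumed.** No true effect for the type I error figures; values missing at random; missing values split 2+1, 4+2 or 7+3 between vitamin D and placebo; visit correlation 0.5-0.9 and CV 0.2-0.3 where raw values are filled; response judged at 6 months.

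**1. The plan's own figures.** The normal approximation with continuity correction and equal arms gives 90.7%, 82.1% and 68.0% power at 26, 22 and 18 subjects, close to the stated 90%, 80% and 70%. At the planned 2:1 allocation it gives 85.9%, 74.7% and 58.2%. That is a separate matter, but it confirms which test was meant.

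**2. Change score filled with the arm mean (exact).** With m1 and m2 observed values, the ratio of reported to correct standard error is

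ratio = sqrt{ [(m1+m2-2)/28] x (1/20+1/10) / (1/m1+1/m2) }

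and type I error = 2 x P(T with m1+m2-2 df > ratio x 2.048), where 2.048 is the 5% critical value on 28 df.

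| Missing | m1, m2 | df | Ratio | Ratio x 2.048 | Type I error |
|---|---|---|---|---|---|
| 2+1 | 18, 9 | 25 | sqrt(0.893 x 0.150/0.167) = 0.896 | 1.836 | 7.8% |
| 4+2 | 16, 8 | 22 | sqrt(0.786 x 0.150/0.188) = 0.793 | 1.624 | 11.9% |
| 7+3 | 13, 7 | 18 | sqrt(0.643 x 0.150/0.220) = 0.662 | 1.357 | 19.2% |

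**3. Raw 6-month value filled, then percent change taken from the participant's own baseline.** Each filled participant's baseline still varies, so the inflation is smaller. Simulation with lognormal visits (40,000 null trials per setting) gives about 5-6% at 2+1, 6-8% at 4+2 and 8-10% at 7+3. With truncated-normal visits (correlation 0.5-0.85) it is 7-9% at 7+3.

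**4. Alternatives under the null.** Observed values only: 4.7-5.1%. LOCF where drop-outs have a month-3 value: 4.7-5.2%. REML model on all observed values (compound symmetry, Satterthwaite df, 10,000 null trials per setting): 4.5-5.3%. The excess belongs to group-mean filling, not to LOCF.

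**5. Primary responder analysis (full binomial enumeration, continuity-corrected chi-square).** Power is 92.1% with nobody missing.

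| Missing | Completers only | Missing = non-response |
|---|---|---|
| 2+1 | 88.9% | 85.4% |
| 4+2 | 80.4% | 76.0% |
| 7+3 | 69.9% | 50.3% |

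For LOCF, give each participant a one-third chance of being missing at 6 months. Let h be the share of drop-outs with a month-3 value, with the same response rates at that visit. A participant with no month-3 value has 0% change and is a non-responder, so each response rate is multiplied by (2/3 + h/3). For h = 0 the rates are 50% vs 6.7% and power is 53.0%. For h = 0.25 it is 66.8%. For h = 0.5 the rates are 62.5% vs 8.3% and power is 77.6%. For h = 0.75 it is 85.8%.

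**The case against.** The strongest defence is that group-mean filling never leads. It is the last of the additional fills, its results are only to be compared with others, and the affected analysis is secondary in a 30-person pilot. With three values missing and the raw value filled, the error is barely above 5%. The 19.2% needs both the drop-out ceiling and filling of the change score, which the text does not specify. All of this stands and limits the weight of the point. It does not rescue the method, because the inflation has the same direction in every setting and leaving the method out loses no information.

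A reader might go further and infer three things that the documents do not support.

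- *That the primary analysis has no missing-data rule, so its power swings by 17 to 20 points.* The missing-data text opens generally, names LOCF first and exempts nothing. The drop-out allowance in the Power analysis does not define an analysis set. The gap (69.9% against 53.0% or 50.3%) arises only at the 33% ceiling, when every drop-out leaves before month 3 or is counted as a non-responder. If half have a month-3 value, LOCF gives 77.6%, above completers. At 4+2 missing, completers and non-response differ by 80.4 - 76.0 = 4.4 points.
- *That missing should count as non-response in the primary analysis.* This discards observed month-3 results and is not safe under unequal drop-out. With 1/20 vs 4/10 missing and equal true response in both arms, false rejection is 5.2% at 50% response, 7.2% at 60% and 13.2% at 75%.
- *That LOCF sets every cognitive drop-out's change to zero.* This follows only from the two-visit schedule in Table 1 and Basic Information, item 1. The Secondary Outcomes list in Research Design and Methods includes a 3-month cognitive test.

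**Conclusion.** The point holds for group-mean filling. As written, the method makes the secondary percent-change ANOVA anti-conservative: 7.8% to 19.2% type I error if the change score is filled, and about 5% to 10% if the raw 6-month value is filled, over 3 to 10 missing values. The first range is exact for normal change scores missing at random. The second also depends on the assumed correlation, CV and distribution. The consequence is a misleading sensitivity result; the primary responder result is not affected.

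The link between LOCF and responder status is a matter of clarity. LOCF is the natural reading, but the plan does not tie it to the responder analysis in words.

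**What to change.** 1. Delete group-mean filling.
2. Run the percent-change ANOVA on observed values.
3. Fit the planned Group by Time model by REML to all observed values, with a Satterthwaite or Kenward-Roger correction. If the plan meant a classical repeated-measures ANOVA, record this as a change of method.
4. In these secondary analyses, keep LOCF and the regression fill as labelled sensitivity analyses.
5. As a minor clarification, state that the LOCF rule sets responder status in the primary analysis, and name the visit at which response is judged. Report completers and missing-as-non-response as sensitivity analyses, not as the primary rule.
6. Reconcile the cognitive testing schedule between the Secondary Outcomes list, Table 1 and Basic Information, item 1.

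The cost is SAP wording and a little analysis time; no new data are needed. In the simulations, mixed-model standard errors exceed those under LOCF by about 4% at 2+1 missing (for example 0.400/0.384) to 16% at 7+3 (0.200/0.172), and the model assumes data missing at random.
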